A.4. Scientific premise. The proposed R21 builds on the strengths and addresses limitations of prior studies. **Strengths.** Lifestyle behavior interventions can prevent EGWG, and EFT improves motivation, emotion, ExF, lifestyle behaviors, and weight management. **Limitations.** Prior lifestyle interventions did not apply FTP, which focuses on motivation, emotion and ExF (critical concepts for promoting healthy lifestyle behaviors and health outcomes). Also, they were too prescriptive and time-consuming for participants (difficult to scale and sustain in practice). Prior EFT studies were mainly conducted in lab and only applied episodic simulation. We propose a 20-week self-directed, web-based intervention (35-40 min/week) and include three forms of EFT: episodic simulation, intention (goal setting), and planning (organization of steps for accomplishing a goal).⁹⁶ Our intervention will efficiently apply GOEFT to address motivation, emotion, ExF, lifestyle behaviors and health outcomes (C.3.6). This proposed study will add scientific knowledge in design and delivery of lifestyle interventions aimed to prevent EGWG in overweight or obese pregnant women.

A. Research Design

This proposed pilot randomized controlled trial (RCT) aims to (1) determine feasibility of the GOEFT intervention and investigate the potential efficacy of the intervention on (2) GWG and maternal and birth outcomes, (3) lifestyle behaviors, and (4) motivation, emotion, and cognition. We will enroll 90 overweight or obese pregnant women (50% White, 50% minority). All measures will be assessed at baseline (T1, ≤15 week-gestation), at 24-27 week-gestation (T2) and at 35-37 week-gestation (T3)

B. Sample

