Inclusion criteria. Participants must be pregnant women ≤ 13 week-gestation with a single fetus as assessed by ultrasound (Research staff or [name], Co-I, a board-certified Ob/Gyn at a collaborating clinic will verify eligibility from the patient's Electronic Health Record, EHR). Participants must also have self-reported (1) pre-pregnancy body mass index (BMI) of 25.0-45.0 kg/m² and height (we will use height and weight to compute body mass index). (2) ability to read and speak English, (3) age of 18-45 years, (4) access to a working smart phone with unlimited text messaging (89 to 94% of American adults aged 18 to 49 years own a smart phone)⁹⁷ and access to internet and (5) receipt of prenatal care and from our collaborating clinics and plan to deliver the baby at The Ohio State University (OSU) Wexner Medical Center, 6) a resident of Franklin Count, and (7) committed to the 20-week intervention.

Exclusion criteria. Self-reported (1) history of ≥ 3 miscarriages, (2) planned termination of the pregnancy, (3) diagnosed hypertension and type 1 or 2 diabetes, (4) history of or current diagnosis of an eating disorder, (5) serious current physical disease (e.g., renal disease or cancer), (6) past bariatric surgery, (7) current or history of substance abuse in the past 6 months, (8) current treatment for a serious psychological disorder (e.g., schizophrenia and bipolar disorder) or (9) contraindications to walking. Consented women will become not eligible to participate in the study if they are not randomized by 16-week 6 days gestation (see D. Detailed Study Procedure: Recruitment and enrollment)—this is because the study intervention starts ≤ 17 weeks gestation. Also, women will become not ineligible for participation if they did not complete the baseline data (T1): online survey via REDCap, two 24-hour dietary recall and wear the Actigraph monitor for at least 4 consecutive days with 6 hours per day.

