Sample size/power. Our primary outcome variable is weekly gestational weight gain (GWG). A final sample size of 72 women (36 per group, after accounting for 20% attrition from the 90 enrolled) will have 80% power to detect a time-averaged between-group difference in weekly GWG with a medium effect size (standardized between-group difference of 0.6). This effect size is translated to a between-group difference of 0.33 lb in weekly GWG, assuming a common standard deviation of 0.55 lb (or 0.25 kg) based on previous research.²⁷ The power analysis was conducted using mixed-effect linear modeling with a two-sided significance level of 0.05, assuming a correlation of 0.7 between the two weekly GWG measures. Due to the pilot nature of the study, our sample size is not powered to detect smaller effect sizes (<0.6). Nevertheless, we will report point estimates, effect sizes, and 95% confidence intervals. These estimates along with clinical significance will guide the results interpretation and sample size determination for a future full-scale RCT (R01).

C. Measurement/ Instrumentation

All participants will be assessed at ≤ 16 week-gestation (T1), 24-27 week-gestation (T2) and 35-37 week-gestation (T3). Survey data will be collected online using password-protected security-ensured Research Electronic Data Capture (REDCap), a secure web application for building and managing online surveys and databases. Primary and secondary outcomes will be extracted from electronic health record. An incentive of \$40 will be provided for participation in each point of data collection for all measurements.

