Feasibility. We will use our tracking records to assess recruitment, randomization and retention. To assess intervention implementation, we will extract data from our study web site that will track and capture details about all activities (e.g., amount of and type of activities completed and % of participants used type in box). We will record the attendance of individual coaching session. Intervention participants will report their motivation and barriers preventing them from engaging in the intervention activities and evaluate the usefulness of with each EFT intervention component. We will also use semi-structure interview questions (up to 20 minutes/an individual interview via zoom) to ask participants to evaluate the intervention. We will use website tracking data, individual coaching session, and results of phone interview to revise the intervention contents for a future large scale intervention study.

Primary outcome: GWG (in lbs). Body weight or gestational weight gain will be extracted from participants' electronic health record.

To compute weekly GWG, we will subtract the measured weights between two adjacent time points (T2 vs. T1; T3 vs. T2) then divide by the number of weeks between the two time points. The IOM recommends that overweight women (BMI 25.0-29.9) be limited to total GWG of 15-25 lbs and obese women (BMI ≥ 30.0) to 11-20 lbs.⁹ To compute the total GWG, we will subtract the self-reported pre-pregnancy weight from weight measured at T3. A woman will be identified as having excessive gestational weight gain if her total gestational weight gain exceeds the Institute of Medicine's criteria.

Secondary outcomes: gestational diabetes, gestational hypertension, mode of delivery, length of labor, apgar score, new born body weight, and premature baby will be accessed by [name] (Co-I) or research staff from the participants' electronic health record.

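### Does leaving the T1 weight untied to randomization materially dilute the weekly weight-gain comparison?

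*Combined protocol and SAP*

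**What the plan says.** Section C (Measurement/Instrumentation, Primary outcome) defines the outcome: "To compute weekly GWG, we will subtract the measured weights between two adjacent time points (T2 vs. T1; T3 vs. T2", each difference divided by the weeks between the two weights.

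The timing of T1 is stated twice. Section A (Research Design) has "All measures will be assessed at baseline (T1, ≤15 week-gestation), at 24-27 week-gestation (T2". Section C has "All participants will be assessed at ≤ 16 week-gestation (T1". Neither gives a lower limit.

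The latest randomization is in section B (Exclusion criteria): "Consented women will become not eligible to participate in the study if they are not randomized by 16-week 6 days gestation". The same paragraph makes a woman ineligible "if they did not complete the baseline data (T1): online survey via REDCap, two 24-hour dietary recall and wear the Actigraph monitor" for the required days. Weight is not on that list.

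The source of the weight also appears in two forms. Section C says "Primary and secondary outcomes will be extracted from electronic health record" and, under the primary outcome, "Body weight or gestational weight gain will be extracted from" the record. Yet the Lifestyle behaviors paragraph of section C has study staff weigh the woman when the Actigraph is returned, and section E trains data collectors to measure body weight. Section D (Usual care) puts clinic visits a month apart until 28 weeks. Randomization takes place at the second Zoom meeting in one part of section D and at a clinic visit in the Intervention implementation part.

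The sample-size paragraph of section B claims "80% power to detect a time-averaged between-group difference in weekly GWG with a medium effect size": 0.33 lb per week, with 36 women per group.

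**The concern.** The effect of interest begins at randomization, but the first rate begins at T1. If the T1 weight is older than the randomization date, the first rate averages untreated and treated weeks. The two arms cannot differ because of treatment in the untreated weeks, so the first-interval difference shrinks and the time-averaged difference shrinks by half as much.

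On the face of the text the gap could be sizeable. For a woman randomized at 16w6d, a limit of 15w0d implies at least 13 days and a limit of 16w0d at least 6 days. With monthly record weights it could reach several weeks. The reverse is also possible: a woman randomized before the T1 limit could have an in-window record weight taken after allocation.

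Two things seem to be at stake. One is whether the power claim survives. The other is whether the pilot estimate, which section B says will help size a full-scale trial, would be too small for that purpose.

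**Working it through.** **Inputs from section B (Sample size/power).** Difference 0.33 lb/week, SD 0.55 lb, correlation 0.7 between the two rates, 36 per group, two-sided 0.05. From sections A to C: T2 at 24–27 weeks and latest randomization at 16w6d (16.86 weeks).

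**The plan's own figure.** SD of the average of two rates = 0.55 × √((1 + 0.7)/2) = 0.507 lb. SE of the group difference = 0.507 × √(2/36) = 0.1195 lb. The 95% half-width is 1.96 × 0.1195 = 0.234 lb. Power for 0.33 lb is 78.8%, so the stated 80% is reproduced to within rounding.

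**Dilution for a given gap.** Let R be gestational age at randomization and g the weeks from the T1 weight to R. The treated share of interval 1 is f = (T2 − R)/(T2 − R + g). The first-interval difference is 0.33 × f, the time-averaged difference is 0.33 × (1 + f)/2, and the shift is 0.33 × (1 − f)/2. This reads 0.33 lb as the effect per treated week, present in full from day one.

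The documents do not give the gaps, so a range is assumed: spread evenly over 0–1 week (study-measured weight) or 0–4 weeks (monthly record weight). The mean of f over gaps from 0 to G is (L/G) × ln((L + G)/L), with L = T2 − R. Example with R = 16w6d and T2 = 25.5: L = 8.643. For G = 4, f = 0.822 and the shift is 0.029 lb. For G = 1, f = 0.946 and the shift is 0.009 lb.

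| Randomized at | Gaps 0–1 week | Gaps 0–4 weeks |
|---|---|---|
| 16w6d | 0.008–0.011 lb | 0.026–0.034 lb |
| 14w0d | 0.006–0.008 lb | 0.021–0.026 lb |

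Ranges run over T2 = 27 down to 24 weeks.

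**What a rule would recover.** The test of a change is how much of this dilution it removes. A simulation of 400,000 women (visits every 4 weeks at a random phase) compared the latest visit on or before both the T1 limit and R with the latest visit on or before R.

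| Randomization | Limit 16w0d | Limit 15w0d | Left after the rule |
|---|---|---|---|
| Spread over 14w0d–16w6d | 0.001–0.002 lb | 0.006–0.008 lb | 0.023–0.030 lb |
| All at 16w6d | 0.009–0.012 lb | 0.019–0.023 lb | 0.026–0.034 lb |
| All at 14w0d | 0 | 0 | 0.021–0.026 lb |

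If the limits mean completed weeks (15w6d and 16w6d), the spread case gives about 0.002 lb and 0. Against the 0.234 lb half-width, the spread case runs from nil to about 3% (0.0075/0.234), and the extreme case reaches about 10% (0.0227/0.234).

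**Consequence for a later trial.** Completers per arm at 80% power = 2 × (1.96 + 0.8416)² × 0.55² × 0.85/d². This is 37.1 (38) for d = 0.33 and 44.8 (45) for d = 0.30. That contrast looks important, but with the rule in place and randomization spread, the estimate is still 0.300–0.307 lb, which gives 43–45 per arm. In the spread case the rule changes the unrounded size by 0.4–0.5 per arm (limit 16w0d) or 1.8–2.3 (limit 15w0d). Most of the dilution comes from monthly weighing, and a definition cannot remove it.

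**Study-measured weight.** The message schedule in section C lists Actigraph pick-up before the second Zoom meeting, where section D places randomization. A weight taken at that return is normally already the last study weight before allocation, so a rule changes essentially nothing.

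**The case for a change.** The strongest case for a change is that the baseline of the primary outcome is undefined under the health-record reading, so two analysts could compute different values from the same records. With no lower limit on T1, an abstractor might pick a visit older than the latest one, and the loss would then exceed the figures above. With 0.33 lb as the effect per treated week, randomization at 16w6d, T2 at 25.5 weeks and T1 at 15w0d, f = 8.643/10.5 = 0.823. The average difference is then 0.301 lb and power 71%. With T1 at 13w0d the figures are 0.279 lb and 65%. A one-sentence rule would cost almost nothing.

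Part of this stands. The rule is not written down, the T1 limits disagree, and the weight source and randomization setting are each described in two ways.

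The power losses do not stand as a criticism. They need 0.33 lb to be a per-treated-week effect. Section B describes it as a time-averaged difference in weekly gain, and section C computes weekly gain from T1, so the natural reading is the outcome as computed. On that reading the gap does not change power. The losses also put every woman at the latest permitted randomization. Choosing an old weight, or one taken after allocation, when a nearer weight before randomization is on file is not what a competent analyst would do. The absence of weight from the eligibility list is weak evidence too: that list covers tasks the woman completes herself, and section A says all measures are taken at baseline.

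**Conclusion.** The observation is accurate, but it identifies a missing detail that ordinary practice fills. No change to the plan is needed. Any bias is toward zero, arises before allocation in both arms, and leaves type I error and the T2–T3 rate untouched. Section F estimates the difference at each time point, so the unaffected interval will be visible separately.

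Writing the rule in advance would gain 0–0.008 lb per week if randomization is spread over 14w0d–16w6d, nothing if all women are randomized at 14w0d, and at most 0.023 lb if all are randomized at 16w6d, against a half-width of 0.234 lb. About 0.02–0.03 lb would remain whatever the rule. If study staff measure the weight, the gain is close to nil.

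These sizes rest on assumed monthly visits at random phase, an assumed earliest randomization of 14w0d, and a full effect from day one. Earlier randomization or a gradual onset would make them smaller. The two T1 limits, two weight sources and two randomization settings are drafting slips that can be reconciled at any routine revision. They do not put the primary comparison or the stated power in doubt.

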Usual care. All study participants will receive usual prenatal care from their obstetrician or midwife. The usual prenatal care visit occurs monthly until 28 week-gestation, every other week from 28-36 week-gestation and weekly from 36-week until delivery. At our collaborating clinics, pregnant women are weighed at each prenatal visit and will receive additional healthy eating counseling, e.g., if they have GDM. To improve retention of women randomly assigned to the usual care group, we will email study newsletters every other month with general information about pregnancy-related health (e.g., over-the-counter medication).

Intervention: A self-directed, web-based GOEFT lifestyle behavior intervention (tailored to participants' needs). ***Intervention mode.*** Intervention participants will receive all aspects of usual care plus a self-directed, web-based GOEFT lifestyle behavior intervention. Previous self-directed, web-based interventions have effectively promoted weight management in overweight or obese adults.¹²³⁻¹²⁵ Also, EFT has been delivered on the web and shown promise for promoting weight management.^{63,126} ***Intervention duration, dosage and topics.*** The intervention will last 20 weeks (start \leq 17 weeks gestation), a duration effectively preventing EGWG in overweight or obese women.²⁰⁻²⁸ Intervention participants will complete weekly online activities (35-40 min/week) via their smart phone or internet access from any location. The intervention includes *three topics*: stress management, healthy eating, and PA (Figure 2). ***Intervention (long-term) goals.*** Participants are strongly encouraged to (1) daily manage stress and emotional reactions using positive strategies, (2) daily eat a diet low in fat and consume less sugary drinks, (3) daily eat a diet high in fruits and vegetables, and (4) walk at a brisk pace for 30 min most days a week.¹²⁷

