complete ≥ 12 weekly intervention activity with $\geq 80\%$ weekly activities completed; 75% of women will be able to generate good quality of steps to achieve their chosen goals; 80% will use the pre-written goals instead of type in (intervention implementation). **Aim 2**, we will first use descriptive statistics and trend plots to summarize and visually compare the weekly gestation weight gain over time. Mixed-effects linear modeling will be used to model the weekly GWG as a linear function of treatment (intervention vs. usual prenatal care care), time, and treatment by time interaction. From the model, we can derive estimates of the time-averaged weekly gestational weight gain for each group, the between-group difference in weekly gestational weight gain at each time point and adjust for within-subject clustering from repeated measures and covariates (e.g., race). We will use logistic regression to estimate the between-group (intervention vs. usual care) difference in the probability of having a binary outcome (for example, excessive gestational weight gain, gestational hypertension, new born body weight), adjusting for covariates (e.g., race). **Aims 3 and 4**, mixed-effects linear modeling will be used to model each continuous outcome (dietary intakes, PA, and psychological eating for Aim 3; motivation, emotion and cognition for Aim 4) as a linear function of treatment, time, and the treatment by time interaction. The intervention effects will be estimated by between-group comparisons of change in the outcome (e.g., healthy lifestyle behaviors) from baseline. Again, we will adjust for within-subject clustering from repeated measures and covariates (e.g., race) in the mixed-effects regression models. **Missing data**. We will carefully examine the pattern of missing data and conduct appropriate multiple imputation if missing at random is indicated. The mixed-effects modeling allows for missing at random. If missing not at random exists, pattern mixture modeling will be used. Sensitivity analysis will evaluate the robustness of study findings without multiple imputation vs. those with imputation or from pattern-mixture modeling.

Zoom IRB Boilerplate:

Zoom is a secure, user-friendly, cloud-based enterprise videoconferencing service that Ohio State University implemented in 2018. Zoom is accessible to faculty and staff at all Ohio State campuses via <https://carmenzoom.osu.edu> .

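### Both weekly gain rates need the T2 weight, so a woman with T1 and T3 weights but no T2 drops out of the primary mixed model although her average weekly gain is known

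*Combined protocol and SAP*

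**What the plan says.** Section C (Primary outcome: GWG) takes body weight from the electronic health record (EHR) and builds two weekly rates per woman: "we will subtract the measured weights between two adjacent time points (T2 vs. T1; T3 vs. T2) then divide by the number of weeks" separating them. Section F (Aim 2) then states: "Mixed-effects linear modeling will be used to model the weekly GWG as a linear function of treatment", time and their interaction. From that model it derives a time-averaged rate per group and the group difference at each time point.

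Section B (Sample size/power) rests on the time average: 36 women per group "will have 80% power to detect a time-averaged between-group difference in weekly GWG".

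Three other passages bear on the point:

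- Section F, Aim 1, defines retention by a weight at T3 alone.
- Section F, Missing data, offers multiple imputation if the data look missing at random, and pattern-mixture modelling otherwise. It does not say what is imputed.
- Section D (Usual care) says that at the collaborating clinics "pregnant women are weighed at each prenatal visit", with visits monthly until 28 weeks and more often afterwards.

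**The concern.** The weights are reduced to differences before they are modelled, and the middle weight enters both differences. The plan is therefore asymmetric. A woman without T3 keeps one rate, while a woman without T2 keeps none, even though her T1 and T3 weights determine the average on which the trial is powered. She would count as a retention success and still have no primary outcome value.

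The statement that mixed models allow for data missing at random does not cover her. A woman with no observed outcome adds nothing to the likelihood, whatever the missingness mechanism. At stake is some precision. If women who miss T2 gain differently from the others, the estimate could also shift, but the documents give nothing from which to size that.

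**Working it through.** **1. The plan's own power.** Inputs from section B: "between-group difference of 0.33 lb in weekly GWG", SD 0.55 lb, "standardized between-group difference of 0.6", correlation 0.7 between the two rates, 36 per group, "two-sided significance level of 0.05".

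- Effect size: 0.33/0.55 = 0.6, as stated.
- SD of the mean of two rates: 0.55 × √((1 + 0.7)/2) = 0.507.
- Standard error of the group difference: 0.507 × √(2/36) = 0.1195.
- Power: Φ(0.33/0.1195 − 1.96) = Φ(0.80) = 78.8% (77.7% with the noncentral t).

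This agrees with the stated 80% to within rounding of method.

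**2. Who contributes.**

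| Weights present | Rates available to the model |
|---|---|
| T1, T2, T3 | both |
| T1, T2 | first only |
| T2, T3 | second only |
| T1, T3 | none |

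With equal intervals of L weeks, the mean of the two rates is ½[(W2 − W1)/L + (W3 − W2)/L] = (W3 − W1)/(2L). W2 cancels, so the last row of the table carries the whole time average. With unequal intervals this is nearly so. Taking T1 at 14 weeks (assumed) and T2 and T3 at their window midpoints (25.5 and 36), the intervals are 11.5 and 10.5 weeks, and the first has weight 11.5/22 = 0.523. The SD of (W3 − W1)/22 is then 0.55 × √(0.523² + 0.477² + 2 × 0.7 × 0.523 × 0.477) = 0.5072, against 0.5071 with equal weights.

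**3. Cost of losing these women.** The T2-only missing rate is an assumption, applied within the 36 per group and before any imputation.

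| T2 only missing | Women per group | Standard error | Power if lost | Power if kept through T3 − T1 |
|---|---|---|---|---|
| 0% | 36.0 | 0.1195 | 78.8% | 78.8% |
| 5% | 34.2 | 0.1226 | 76.8% | 78.8% |
| 10% | 32.4 | 0.1260 | 74.5% | 78.8% |
| 20% | 28.8 | 0.1336 | 69.5% | 78.8% |

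**4. The favourable end.** The 36 per group already excludes 20% attrition: 90 × 0.20 = 18, or 9 per group. Suppose all 9 leave after T2 and supply the first rate.

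- The information matrix per group, in units of 1/0.55², is 36 × R⁻¹ + 9 × diag(1, 0), where R is the 2 × 2 matrix with correlation 0.7. This has diagonal 79.6 and 70.6 and off-diagonal −49.4.
- The variance of the time average is 0.55² × 0.0196 = 0.00593 per group.
- The standard error of the difference is √(2 × 0.00593) = 0.1089, and power is Φ(0.33/0.1089 − 1.96) = 85.8%.

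With T2-only loss of 5%, 10% and 20% the same calculation gives 84.3%, 82.7% and 79.0%. If those women are kept, power stays at 85.7 to 85.8%.

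**5. What the other clinic weights would add.** Assume a between-woman slope SD of 0.45 lb/week, an interval-specific SD of 0.15 and a visit-to-visit weight error SD of e lb.

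- Each rate has variance 0.45² + 0.15² + 2e²/L², and the covariance of the two rates is 0.45² − e²/(11.5 × 10.5).
- At e = 2 the variances are 0.286 and 0.298 and the covariance is 0.169. The rate SDs are about 0.53 and 0.55, and the correlation is 0.58.
- In simulation at e = 2, the per-woman variance is 0.232 for the adjacent-rate average and 0.223 for a slope on all visits: 0.232/0.223 = 1.04, a 4% gain. At e = 1 the gain is about 1%.
- Errors of 3 and 4 lb give larger gains, but they imply rate correlations of 0.34 and 0.14 against the stated 0.7.

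**The case against.** The strongest reply is that T2 will seldom be missing. If weights come from the EHR and visits are monthly until 28 weeks, most women with a T3 weight will also have one in or near the 24-27 week window, and section D (Cohort retention) allows collection windows to be extended. Imputing a T2 weight from T1 and T3 would recover the rest. Much of this stands, and it is why the size of the problem is uncertain. It is not written down, however. No rule says which clinic weight serves as T2 or what happens when none falls in the window. Sections C (Lifestyle behaviors) and E (Measures) describe weights taken by study staff, which does not fit EHR extraction and would make a missed T2 likelier. Imputing rates rather than weights could ignore the woman's known T1-to-T3 change.

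A reader might infer three stronger points that the documents do not support:

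- **That the trial has no power to spare.** This is true only if the women lost to attrition contribute nothing. If they supply a first rate, power stays above 80% even at 10% T2-only loss.
- **That giving unequal intervals equal weight is a defect.** It is a choice of estimand. Across plausible visit timings (T1 from an assumed 10 weeks), weighting by duration leaves power at 77.6 to 78.8%.
- **That using every clinic weight would bring a large gain in efficiency.** Under inputs near the protocol's SD and correlation, the gain is a few percent.

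**Conclusion.** The concern holds in a limited form. As written, a woman with T1 and T3 weights but no T2 has no primary outcome value, although she is counted as retained and her average gain is known. The planned imputation may recover her, but it is conditional and its target is unspecified.

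With 36 per group, the cost before imputation is 2.0 points of power at 5% T2-only loss (78.8% to 76.8%) and 4.3 points at 10% (to 74.5%). With the women lost after T2 included, the corresponding losses are 1.5 points (85.8% to 84.3%) and 3.1 points (to 82.7%). The missing rates are assumptions, and the true loss could be close to nil if nearby EHR weights are accepted as T2. Total GWG and the excessive-gain classification are not affected, because they use the pre-pregnancy and T3 weights. This is a modest weakness, worth correcting because it is cheap to avoid.

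**What to change.** Fit the primary mixed model to the T1, T2 and T3 weights, not to the two rates:

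- Use exact gestational age as the time scale, piecewise linear with a knot at T2 (a fixed gestational week within the T2 window, named in advance), with treatment-by-week terms for each segment, adjustment for race and a stated within-woman covariance.
- Report the two interval-specific differences and their time average in lb/week, and state how the average is weighted.
- Keep the adjacent-rate model as a sensitivity analysis.

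If the rate model stays primary, state at minimum that weights rather than rates are imputed, or that (T3-T1)/weeks is used when T2 is missing.

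In either case, reconcile the passages on the source of the weights, name the rule that selects the T1, T2 and T3 weights, and report how many women have T3 but no T2. A model using all EHR clinic weights is an optional supporting analysis. It leans more on linearity, and the visit schedule concentrates weights late in pregnancy.

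The cost is SAP wording, a little more analysis work and a piecewise-linear assumption. No extra data are needed for the main change.
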